9.3 Acquisition of outcome measures

- Non-invasive longitudinal in vivo measurement of the gastrocnemius muscle by MSOT and subsequent 3D reconstruction of the 2D scans
- Non-invasive static 2D in vivo measurement of the gastrocnemius muscle by MSOT
- Acquisition of the flow profile of the common femoral artery and popliteal artery using CCDS
- Acquisition of the ABI
- Acquisition of the current walking distance in meters standardized by treadmill examination (3 km/h with 12% gradient)
- Acquisition of the clinical PAD stage
- Recording of relevant clinical data from the patient's file

9.4 Total duration of the study

According to the number of cases, the expected total duration of the study until inclusion of the last study participant is approximately 6 months. Only one examination session is required per patient.

10 Risk-benefit Analysis

10.1 All study-related risks

Based on the classification criteria for medical devices (Directive 93/42/EEC, Annex IX), the iThera Medical optoacoustic system is Class IIa:

- Active diagnostic device
- non-invasive

- Temporary use (<60 min).

For the present research device (current type designation according to imprint: Acuity Echo), a CE certification has been available since 02/05/2021 and is used exclusively within the intended purpose without invasive measures. There is no dependency relationship with the manufacturer, all diagnostic and analytical procedures are available to the study investigators on site.

This is an "Other Clinical Trial" according to Article 82 of the Medical Device Regulation (MDR) with the aim of answering the scientific question mentioned above. No proof of conformity is provided in the process.

iThera Medical is ISO 13485:2016 certified.

The device has an IP2X rating, the handheld probe has an IPX7 rating, and the foot switch has an IPX6 rating according to IEC/EN 60529.

Compliance with energy limits

Laser safety and maximum allowable radiation dose for laser pulse irradiation is regulated in the ANSI and IEC 60825 laser standards. The MSOT system complies with these standards and therefore remains below the MPE (maximum permissible exposure) limits for skin irradiation and is therefore considered safe.

Temperature increases due to MSOT in tissue

Optoacoustic imaging does not result in a significant increase in tissue temperature. Absorption of a laser pulse in tissue results in a local transient temperature increase of a few millikelvin. Depending on the duration of the examination and the patient's skin type, temperature increases typically in the range of less than one degree Kelvin.

Histological changes in the tissue

Histological changes in the target tissue and surrounding structures are not expected, nor have they been observed in previous preclinical and clinical studies.

Only slight, reversible reddening or heating is to be expected in sensitive skin.

Such adverse effects may be noticed by the subject or physician at any time; the study may then be interrupted or discontinued. In any case, no irreversible damage is to be expected.

In principle, the near infrared light used in MSOT can cause retinal damage if the eye is irradiated. To prevent this, study participants and investigators will wear safety glasses during the study.

Since the data obtained will not be used to interpret findings, there is no risk of possible misdiagnosis or misrepresentation of data in this study.

Other risks do not exist in the context of this study and were not observed based on previous data.

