8.2 Number of cases

A valid calculation of the number of cases is not possible because of the novelty of the reconstruction procedure and due to the study design as a pilot study with explorative character. For the exploration of the planned research question, a study collective of 8

study participants is aimed for. Two healthy volunteers, two patients in PAD stage II, two patients in stage III and two patients in stage IV according to Fontaine will be examined. One male and one female will be included per stage to represent both genders.

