The actual current walking distance is used to classify and categorize the severity of PAD and should be recorded by a treadmill examination. Under medical supervision, the patients/probands are to complete the greatest possible distance on the treadmill at a 12% incline and 3 km/h (standard setting). If the 12% incline is not practicable for the patient, the incline will initially be reduced to 6%. If this is also not practicable, it will be reduced to 0% incline. The walking distance is recorded in meters. Since the first 200 meters in particular are important for the classification of PAD, the examination will be terminated by the study physician when a walking distance of more than 500 meters has been reached. The treadmill examination takes about 15 minutes and is usually performed for patients in stage II as part of routine vascular surgery diagnostics. For patients in stage III or IV, the examination is not part of the routine diagnostics and only takes place within the framework of study participation if the study physician declares this medically justifiable.

All examinations mentioned so far take place in the facilities of the Department of Vascular Surgery.

For the MSOT measurements, the CE-certified MSOT device of the Pediatric and Adolescent Clinic of the University Hospital Erlangen is used. Since the MSOT device is located in the facilities of the Children's Hospital, the patients/probands are transported there in a wheelchair after the examinations mentioned so far. It is

important that there is no physical exertion during the transport, as this could falsify the MSOT values. The transport takes about 15 minutes. Subsequently, MSOT measurements are taken with the MSOT device over a length of about 6 cm in the longitudinal section of the medial head of the gastrocnemius muscle (in patients in the area of the affected leg). Multiple measurements of both legs are performed with different foils applied in a standardized manner.

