If necessary, the area of the lower leg to be examined will be shaved to avoid artifacts from dark colored hairs. The ultrasound gel is applied to the calf. Then a foil imprinted with an "N" is applied and fixed. The proband ID is noted on the foil. Above the imprint, an initial static measurement is taken at rest and subsequently a longitudinal measurement is taken, which can be reconstructed in 3D. At least three longitudinal 2D measurements are made or repeated until a promising result is obtained. The same procedure is repeated with a foil imprinted with a trident.

The examination is performed analog to sonography above the corresponding skin layers without further invasive procedures. The anatomical region can be localized by means of built-in B-scan sonography; subsequently, the corresponding optoacoustic signals can be derived. The duration per anatomical region is limited to 5 minutes; the study participants can remain in a relaxed position during the examination; assistance, e.g., breathing maneuvers, is not necessary.

Subsequently, the patient will complete a defined walking distance of 150 meters under medical supervision. The foils printed with tridents remain fixed to the calf muscles for this purpose. Afterwards, the medial head of the gastrocnemius muscle is measured again using MSOT. Therefore, the affected leg of patients is first examined in a static 2D-measurement, then in longitudinal measurements and again in a static 2D-measurement. In healthy probands, the right leg is measured first.

After a second defined walking distance of 150 meters, the unaffected leg is examined in patients and the left leg in healthy probands in the order described above.

In the context of so far unpublished preliminary studies, it was indicated that an active muscle exercise between the two examinations by MSOT causes a change of the perfusion parameters and can possibly unmask a stenosis in the supply area of the lower legs. If the patient is unable to walk 150 meters between the two MSOT measurements due to pre-existing conditions or due to the severity of the PAD stage,

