12.4 Revocation, data deletion

In the event of revocation of the declaration of consent, data collected up to this point can be taken into account and can be continued to be stored. However, the patient has the right to request their destruction, unless legal provisions prevent destruction.

13 Handling of Incidental Findings

The acquisition of all results as well as the evaluation of the ABI and the images from the CCDS are performed for healthy probands only for the purpose of this study and not for general or special diagnostic purposes. Evidence of diseases unknown to the participant may not be detected in these examinations. Incidental findings in patients are rare (routine diagnostics), and the procedure for handling incidental findings applies equally to healthy probands and to patients. If abnormal findings are discovered during the scientific evaluation, an appropriate specialist is consulted for follow-up and reporting of the values and images that were originally determined for research purposes (healthy probands) or in the course of routine diagnostics (patients). Whether a reportable finding exists is decided by the study director according to his professional discretion. All study participants will be informed in advance about any disadvantages of reporting findings as part of the written informed consent.

Such disadvantages are to be understood as

- severe psychological stress due to the knowledge of or the suspicion of a threatening disease
- disadvantages in the case of certain legally significant actions, such as the conclusion of a life or health insurance policy or an employment contract
- further examinations linked to the notification of the findings, which may represent a health risk, even if the further work-up reveals that the findings have no pathological significance

After being informed with regard to the above-mentioned possible disadvantages due to the notification of incidental findings in the context of this study, the proband will put

down in writing whether or not he/she wishes to be informed and advised about such abnormalities.

14 Handling of Biomaterials

Not applicable

15 Proband Insurance

[figure not shown]
A separate proband insurance will be concluded within the framework of an annual contract with the insurer HDI Global SE, Düsseldorf branch. The insurance is based on the agreements according to the "Insurance for clinical trials not subject to compulsory insurance".

16 Signatures

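### Section 10.1 says that no risks exist beyond those it lists, yet Section 9.2 adds exercise done only for the study, and the whole-study stopping rule in 10.3 does not reach a serious exertional event

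*Combined protocol and SAP*

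**What the plan says.** Section 10.1 discusses laser energy limits, tissue heating, histological change, skin reddening and eye exposure. It denies any risk of misdiagnosis and closes with: "Other risks do not exist in the context of this study and were not observed based on previous data". Exercise is not mentioned. Section 10.4 also argues from the measurement alone.

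Section 9.2 describes two kinds of exertion.

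- **Treadmill.** Under medical supervision, "the patients/probands are to complete the greatest possible distance on the treadmill at a 12% incline and 3 km/h". The incline can be lowered for a patient who cannot manage it, and the test ends once 500 m is passed. It "is usually performed for patients in stage II as part of routine vascular surgery diagnostics". In stages III and IV it is not routine and "only takes place within the framework of study participation if the study physician declares this medically justifiable".
- **Exercise before the repeat scans.** First, "the patient will complete a defined walking distance of 150 meters under medical supervision". The other leg is then scanned "After a second defined walking distance of 150 meters". Patients who cannot manage this may drop to 100, 50 or 25 m, or do standing or seated foot exercise for at least two minutes.

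Section 6.2 lists treadmill walking distance twice, once without restriction and once leaving out stages III and IV.

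Section 10.3 ends the whole study only for significant health harm that is both new and caused by the MSOT examination. For an individual, it ends participation for skin heating or redness, or if the exercise between scans cannot be done, with breathlessness as one example.

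**The concern.** A section that claims to be complete leaves out a class of risk that the same protocol guards against elsewhere. Medical supervision, a physician's decision before a stage III/IV treadmill test and the mention of breathlessness all make sense only if exertion carries some risk. Section 10.2 says that participants gain no direct benefit, so the risk side of the balance should be stated accurately.

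The second part concerns stopping. If a participant had a serious event on the treadmill or during a walk, the written whole-study criterion would not call for any pause or review. What is at stake is the accuracy of the safety text and its consistency with the procedures. No estimate, test or sample size depends on it.

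**Working it through.** The protocol gives no exertional event rate and none is assumed here. The check sets the sections side by side and counts exposure.

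**1. Who does study-only exercise?**

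Section 8.2 plans "Two healthy volunteers, two patients in PAD stage II, two patients in stage III and two patients in stage IV according to Fontaine", so 2 + 2 + 2 + 2 = 8.

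*Treadmill.* Section 9.2 calls the test usually routine for stage II, so those 2 patients are counted as routine. For healthy volunteers, Section 13 says that the study's results "are performed for healthy probands only for the purpose of this study and not for general or special diagnostic purposes", so their test is study-only.

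| Reading | Study-only treadmill tests | Share of 8 |
|---|---|---|
| The 6.2 bullet excluding stages III/IV governs | 2 healthy | 2/8 = 25% |
| Section 9.2 governs, no stage III/IV patient cleared by the physician | 2 healthy + 0 | 2/8 = 25% |
| Section 9.2 governs, all stage III/IV patients cleared | 2 + 2 + 2 = 6 | 6/8 = 75% |

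The flow chart (Figure 3), which might settle the conflict between 6.2 and 9.2, is not shown in the text reviewed.

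Time to reach the cut-off at the set speed: 0.5 km ÷ 3 km/h × 60 = 10 minutes.

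*Exercise before the repeat scans.* This applies to all 8 participants, since 9.2 names the leg to be scanned for both patients and healthy volunteers.

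- Full distance: 2 × 150 m = 300 m
- Lowest walking step for patients: 2 × 25 m = 50 m
- Standing or seated substitute for patients: 0 m

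This exposure does not depend on how the treadmill conflict is resolved.

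**2. Does 10.1 cover it?**

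No. The risks it accepts come from light and heat. The one other item, misdiagnosis, is denied and has nothing to do with exercise. Its remark that the study may be interrupted refers to skin reddening or heating.

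**3. Does the whole-study criterion in 10.3 cover it?**

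It sets two conditions.

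- *The harm must be new.* A recognised complication of exertion is not.
- *The harm must come from the MSOT examination.* The treadmill test is done beforehand, in a different department. The walks between scans could be read into the examination only by stretching the term, and a known complication would still fail the first condition.

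**4. Which precautions are already in place?**

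Section 8.1 lets the study physician exclude people on safety grounds and requires healthy volunteers to have a normal ABI and no known PAD, diabetes or chronic renal insufficiency. Section 9.2 provides supervision, step-down and physician judgement. Section 10.3 withdraws anyone for whom the exercise between scans is not feasible. These reduce the risk, but they do not make the 10.1 sentence true.

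**The case against.** The best defence is that this is a very small, single-session study with short supervised walks that can be reduced to seated foot movements. The physician can exclude, step down or end the treadmill test, and participants may withdraw at any time. A whole-study rule aimed at the imaging technique is a reasonable choice, and nothing suggests that the study director could not pause recruitment without a written trigger. The consent pages are not available and may already mention exertion.

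Most of this stands, and it is why the point is minor. It does not rescue a sentence saying that no other risks exist, and consent wording would not correct the protocol text.

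A reader might infer three stronger points that the documents do not support.

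- *That exercise is unprotected.* Sections 8.1, 9.2 and 10.3 show otherwise.
- *That 6 of 8 participants will certainly have a study-only treadmill test.* That is a ceiling. It needs Section 9.2 to prevail over the 6.2 exclusion and the physician to clear all four stage III/IV patients.
- *That the individual withdrawal rule has a serious hole.* A treadmill event that still left seated foot exercise feasible would fall outside its wording. But the scenario is narrow, the rule's list of reasons is open-ended, and a physician is supervising.

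**Conclusion.** The point holds as a minor one. The 10.1 statement is incorrect given the exercise in 9.2, and the whole-study criterion in 10.3 does not, on its wording, respond to a serious exertional event. All 8 participants do study-only exercise before the repeat scans. The treadmill is study-only for 2 of 8 if the 6.2 exclusion governs, and for up to 6 of 8 otherwise.

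This rests on counting both stage II patients' treadmill tests as routine and on the text available. It says nothing about how likely an exertional event is or what the consent form discloses. The statistical analysis is unaffected.

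**What to change.** 1. **Section 10.1.** Replace the closing sentence with wording such as: *Further study-related risks are exertional risks from the treadmill test and from the walking or foot exercise. They are limited by the physician's safety exclusion (8.1) and by supervision, stepwise reduction and physician judgement (9.2).*
2. **Section 10.3.** Keep the MSOT criterion as it is and add a separate sentence: *Enrolment is paused for review by the study director if a serious adverse event judged related to any study procedure, including the treadmill test and walking exercise, occurs.* It should stand alone. Attached to the existing sentence, it would make one event require both discontinuation and a pause.
3. **Event record.** Record adverse events during the treadmill test and both exercise bouts, if no such record exists. The available text describes none, but some pages were removed.

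An individual stopping rule for treadmill events is optional. If added, failing to complete the treadmill test should not by itself end participation.

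The cost is a few sentences and a short record, with no extra patients, staff or procedures. The downside is that one related serious event could briefly pause enrolment.

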10.2 Benefits associated with the study

The data obtained in the study may provide essential insights into the blood flow situation in different areas of the calf muscles in PAD. The possibility of non-invasive 3D imaging without the need for administration of contrast medium could open up new aspects in the diagnosis of the disease. There is a purely scientific benefit from the study. There is no direct diagnostic or therapeutic benefit for patients/probands from participation in the study.

10.3 Discontinuation criteria

Discontinuation criteria for the individual participant:

Discontinuation of study participation will occur if there is noticeable heating or redness of the skin. The examination time per anatomical region is limited to 5 minutes, so that these events are highly unlikely.

In addition, study participation will be discontinued in the event of unfeasible muscle exercise described above between both MSOT measurements, e.g. due to dyspnea, orthopedic diseases, etc.

Discontinuation criteria for the entire study:

Discontinuation of the entire study must occur in the event of the occurrence of previously unknown and unobserved significant and adverse health effects from the MSOT examination. This is considered unlikely, since several hundred patients and healthy volunteers have already been examined with this method at the University Hospital Erlangen alone.

10.4 Statement on medical justifiability

Based on previous experience in adult patients, the risk of the occurrence of adverse events is considered to be extremely low. No central organs are examined in this study,

but only measurements on extremities are performed - this leads to a further significant reduction of a possible residual risk. The examination will be performed by persons who are familiar with the device and the measurement method.

11 Statistical Methodologies

Due to the explorative character of the pilot project, mainly a descriptive statistical evaluation of the collected parameters will be performed. A case number of 8 study participants will be chosen to test the feasibility of the 3D method initially. A sample size calculation will not be done. In order to quantitatively classify the results, individual parameters of the study will be compared with values from previous studies on the MSOT procedure in patients with PAD. The MSOT parameters are compared before and after muscle exercise using a paired-samples t-test. The selection of probands will be standardised with one male and one female per stage. Due to the small number of cases, probands who are suitable for MSOT measurements are selected. The criteria include little subcutaneous fat tissue, light skin colour and less hair. Therefore, the selection of probands is not representative of the normal population.

12 Data Management and Data Privacy

12.1 Data acquisition, data storage

All raw data, such as patient records, represent source documents. Their availability is ensured for routine monitoring. Participation of individual patients or probands in the study will be documented and the study director will maintain an independent list for identification of participating probands. This list includes name and date of birth as well as study date and pseudonymization abbreviation of the patients and subjects. The study director is responsible for the quality of data collection and storage. Data storage is exclusively on computers or specially designated network drives of the University Hospital Erlangen.

12.2 Pseudonymization

Before any scientific analysis of the materials and data of this study, all information will be pseudonymized according to the guidelines of the Federal Data Protection Act.

12.3 Data transfer

There are no plans passing the data of this study to third parties and it will not be done; in particular, the manufacturer will not be given access to the data. The study results can be published anonymously, and it will not be possible to infer the identity of the participating persons. The data will be kept for 10 years and then will be destroyed.

12.4 Revocation, data deletion

In the event of revocation of the declaration of consent, data collected up to this point can be taken into account and can be continued to be stored. However, the patient has the right to request their destruction, unless legal provisions prevent destruction.

13 Handling of Incidental Findings

The acquisition of all results as well as the evaluation of the ABI and the images from the CCDS are performed for healthy probands only for the purpose of this study and not for general or special diagnostic purposes. Evidence of diseases unknown to the participant may not be detected in these examinations. Incidental findings in patients are rare (routine diagnostics), and the procedure for handling incidental findings applies equally to healthy probands and to patients. If abnormal findings are discovered during the scientific evaluation, an appropriate specialist is consulted for follow-up and reporting of the values and images that were originally determined for research purposes (healthy probands) or in the course of routine diagnostics (patients). Whether a reportable finding exists is decided by the study director according to his professional discretion. All study participants will be informed in advance about any disadvantages of reporting findings as part of the written informed consent.

Such disadvantages are to be understood as

- severe psychological stress due to the knowledge of or the suspicion of a threatening disease
- disadvantages in the case of certain legally significant actions, such as the conclusion of a life or health insurance policy or an employment contract
- further examinations linked to the notification of the findings, which may represent a health risk, even if the further work-up reveals that the findings have no pathological significance

After being informed with regard to the above-mentioned possible disadvantages due to the notification of incidental findings in the context of this study, the proband will put

down in writing whether or not he/she wishes to be informed and advised about such abnormalities.

14 Handling of Biomaterials

Not applicable

15 Proband Insurance

[figure not shown]
A separate proband insurance will be concluded within the framework of an annual contract with the insurer HDI Global SE, Düsseldorf branch. The insurance is based on the agreements according to the "Insurance for clinical trials not subject to compulsory insurance".

16 Signatures

